## 3.5 Subgroup Analyses

A sub-study taking place in Bulgaria and Moldova was added to the clinical study protocol. The substudy was added to investigate if the effect of AP1189 in newly diagnosed subjects with severe RA who are to start up-titration with methotrexate is comparable in these two countries compared to the main study. In addition to analyzing the main study and the sub-study separately, all data will be pooled to investigate the overall effect in all participating countries.

## 3.6 Data Transformation and Derived Variables

## Demographic analysis

Age at inclusion (years) will be calculated from date of birth and screening date.

## Efficacy analysis

The HAQ-DI scale will be scored in accordance with Bruce and Fries, The Health Assessment Questionnaire (HAQ), *Clinical and Experimental Rheumatology*, 2005. Maska et al. summarize the scoring procedure as below (see https://onlinelibrary.wiley.com/doi/full/10.1002/acr.20620): "1) identify the highest subcategory score from each of the 8 categories. Adjust for use of aids/help by increasing the category score from 0 or 1 to a 2 if use of aids/help for that category (utilize table of companion aids/help for HAQ categories). If the category score is already a 2 or 3, no adjustment is made; 2) sum the category scores; and 3) divide the final sum by the number of categories answered to obtain the final HAQ score rounded to the nearest value evenly divisible by 0.125. Requires a minimum of 6 categories answered; if less, do not score."

The FACIT-Fatigue total subscale will be scored in accordance with http://www.ser.es/wp-content/uploads/2015/03/FACIT-F\_INDICE.pdf.

Change from baseline to week 4 (value at week 4 minus value at baseline) will be calculated for the following variables:

- CDAI
- DAS28
- HAQ-DI total score
- FACIT-Fatigue total subscale score
- number of swollen and/or tender joints (summarizing SJC and TJC)
- CXCL13
- IL-1β
- IL-6
- IL-10
- IL-6/IL-10 ratio
- TNF-α

In addition, percent change from baseline to week 4 (change from baseline as defined above divided by the baseline value) will be calculated for the following variables:

- CXCL13
- IL-1β
- IL-6
- IL-10
- IL-6/IL-10 ratio
- TNF-α

Indicators noting the following will be constructed, based on the above defined change in CDAI score from baseline to week 4:

- a 5-point decrease
- a 10-point decrease
- a 15-point decrease
- a 20-point decrease
- a 30-point decrease

Indicators noting a change in CDAI score will be constructed as follows:

- from severe (CDAI > 22) to moderate or lower (CDAI ≤ 22) at week 4 compared to baseline
- from severe (CDAI > 22) to low or remission (CDAI ≤ 10) at week 4 compared to baseline
- from severe (CDAI > 22) to remission (CDAI ≤ 2.8) at week 4 compared to baseline

Indicators noting a change in DAS28 will be constructed as follows:

- from > 3.2 to  $\leq$  3.2 at week 4 compared to baseline
- An indicator noting a change in DAS28 from high (DAS28 > 5.1) to moderate or lower (DAS28 ≤ 5.1) at week 4 compared to baseline

For the calculation of ACR response rates, indicators noting the following will be constructed:

- ≥20% improvement (reduction) in swollen and tender joint counts (SJC and TJC summarized) at week 4 compared to baseline
- ≥50% improvement (reduction) in swollen and tender joint counts (SJC and TJC summarized) at week 4 compared to baseline
- ≥70% improvement (reduction) in swollen and tender joint counts (SJC and TJC summarized) at week 4 compared to baseline
- ≥20% improvement (reduction) in Patient's Global Assessment of Disease Activity (dataset VAS) at week 4 compared to baseline
- ≥50% improvement (reduction) in Patient's Global Assessment of Disease Activity at week 4 compared to baseline

Study SynAct-CS002 – Statistical Analysis Plan

- ≥70% improvement (reduction) in Patient's Global Assessment of Disease Activity at week 4 compared to baseline
- ≥20% improvement (reduction) in Physician's Global Assessment of Disease Activity (dataset VAS) at week 4 compared to baseline
- ≥50% improvement (reduction) in Physician's Global Assessment of Disease Activity at week 4 compared to baseline
- ≥70% improvement (reduction) in Physician's Global Assessment of Disease Activity at week 4 compared to baseline
- ≥20% improvement (reduction) in Patient's Assessment of Pain at week 4 compared to baseline
- ≥50% improvement (reduction) in Patient's Assessment of Pain at week 4 compared to baseline
- ≥70% improvement (reduction) in Patient's Assessment of Pain at week 4 compared to baseline
- ≥20% improvement (increase) in Health Assessment Questionnaire (HAQ-DI) total score at week 4 compared to baseline
- ≥50% improvement (increase) in Health Assessment Questionnaire (HAQ-DI) total score at week 4 compared to baseline
- ≥70% improvement (increase) in Health Assessment Questionnaire (HAQ-DI) total score at week 4 compared to baseline
- ≥20% improvement (reduction) in C-Reactive Protein (CRP) at week 4 compared to baseline
- ≥50% improvement (reduction) in C-Reactive Protein (CRP) at week 4 compared to baseline
- ≥70% improvement (reduction) in C-Reactive Protein (CRP) at week 4 compared to baseline

The ACR response rates ACR20, ACR50, and ACR70 are defined as follows (using the indicators above):

≥20%, ≥50% and ≥70% improvement at week 4 compared to baseline, respectively, in:

- Swollen and tender joint counts (SJC and TJC summarized), and 3 of the following 5 assessments:
  - Patient's Global Assessment of Disease Activity
  - Physician's Global Assessment of Disease Activity
  - o Patient's Assessment of Pain
  - Health Assessment Questionnaire (HAQ-DI)
  - C-Reactive Protein (CRP)

The Patient Global Assessment of Disease Activity RA, the Investigator Global Assessment of Disease Activity RA, and the CDAI score will be presented in absolute values and values relative to placebo by dividing the mean, median, min, and max values for each active treatment group by the corresponding value for the placebo group.

An indicator noting whether a subject received rescue treatment (joint injections with corticosteroid) during the 4-week treatment period (Baseline visit to Visit 6) will be constructed. The team will go

Study SynAct-CS002 – Statistical Analysis Plan

through the concomitant medication listings to define which subjects received rescue treatment before analyses.

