14.2 Secondary Efficacy Endpoints

The effects of AP1189 against placebo will be evaluated by assessing the following by treatment group:

- Proportion of subjects achieving a reduction of more than 10 (ten) swollen and/or tender joints (SJC and TJC, summarized) at week 4 compared to baseline
- Proportion of subjects achieving a change in CDAI score at week 4 compared to baseline
 - Proportion of subjects with a 5-point decrease
 - Proportion of subjects with a 10-point decrease
 - o Proportion of subjects with a 15-point decrease
- Proportion of subjects achieving a change in DAS28 from DAS28 >3.2 to DAS28 ≤ 3.2 at week 4 compared
 to baseline
- Change of HAQ-DI at week 4 compared to baseline
- Change of FACIT-Fatigue at week 4 compared to baseline
- Proportion of subjects achieving ACR response assessed by ACR 20, ACR 50, and AC70

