21.3.8 American College of Rheumatology Response Rates

The ACR (American College of Rheumatology) Criteria is a standard criterion to measure the effectiveness of various arthritis medications or treatments in clinical trials for RA.

The ACR response rates ACR20, ACR50, and ACR70 are defined as ≥20%, ≥50% and ≥70% improvement, respectively, in swollen and tender joint counts (SJC/TJC) and 3 of the following 5 assessments: Patient's Global Assessment of Disease Activity (see above), Physician's Global Assessment of Disease Activity (see above), Patient's Assessment of Pain (see above), Health Assessment Questionnaire (HAQ-DI, see above), and C-Reactive Protein (CRP).

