#### 2.1.6 Secondary Efficacy Variables

The secondary efficacy variables are described in 2.1.5 above, with the following addition:

• The number of swollen and/or tender joints are found by summarizing SJC and TJC.

See section 3.6 for details of calculation of secondary efficacy variables.

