### 3.12 Documentation and Other Considerations

Protocol Section 12.2 Primary efficacy Objective states "Effect of AP1189 vs. placebo in subjects with severe active RA (CDAI > 22), undergoing up-titration with MTX, by showing a change in CDAI from severe (CDAI > 22) to moderate (CDAI  $\leq$  22) after 4 weeks treatment compared to baseline." The cut-off values for the CDAI score correspond to severe (CDAI>22) or moderate **or lower** (CDAI  $\leq$  22), which is the wording used in this analysis plan.

Protocol Section *12.3 Secondary efficacy Objectives* states that the "Proportion of subjects achieving American College of Rheumatology (ACR) response assessed by ACR20, ACR50, and ACR70" will be assessed. These responses will be assessed at week 4 compared with baseline (no time point was specified in the protocol).

Protocol Section 12.4 Tertiary Efficacy Objectives states that the "Effect of AP1189 compared to placebo at week 4 compared to baseline on inflammatory and collagen destructive biomarkers" will be assessed. The comparison to baseline will be made by calculating the change for these biomarkers (CXCL13, IL-1 $\beta$ , IL-6, IL-10, and TNF- $\alpha$ ) at week 4 compared with baseline (the calculation of a change from baseline was not specified in the protocol). In addition, the ratio IL-6/IL-10 will be evaluated in the same way.

Protocol Section 23.6 Pharmacokinetic Analyses states that "Descriptive statistics will be used for an exploratory description of exposure in relation to effect." However, only one sample is taken at each visit (for some visits), with variability in the time from last dosing to sampling. Thus, the relationship between exposure and effect is not possible to evaluate, and exposure will therefore be described without relation to effect..

No other changes to analyses specified in the protocol have been identified at the time of writing this SAP.

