| TJC sum (TJCSUM, duplicates in datasets JTS and CDAI)   | n, mean (95% CI), sd, median, min, max,
by visit  |
| Re-entered TJC (28) (TJCENTRY)  | Listing only (used for CDAI calculation)   |
| SJC sum (SJCSUM, duplicates in datasets JTS and CDAI)   | n, mean (95% CI), sd, median, min, max,
by visit  |
| Re-entered SJC (28) (SJCENTRY)  | Listing only (used for CDAI calculation)   |

| Total number of tender or swollen joints (SJC and TJC summarized)   | n, mean (95% CI), sd, median, min, max,
by visit  |
|---|--|
| Proportion of subjects achieving a reduction of
more than 10 (ten) swollen and/or tender joints
(SJC and TJC, summarized) at week 4 compared
to baseline (derived, see Section 3.6)  | # patients and % /category (2 categories:
Achieving/Not achieving reduction)  |
| Proportion of subjects achieving a 5-point
decrease in CDAI score after 4 weeks of
treatment compared to baseline (derived, see
Section 3.6)   | <pre># patients and % /category (2 categories:
Achieving/Not achieving decrease)</pre>   |
| Proportion of subjects achieving a 10-point
decrease in CDAI score after 4 weeks of
treatment compared to baseline (derived, see
Section 3.6)  | # patients and % /category (2 categories:
Achieving/Not achieving decrease)   |
| Proportion of subjects achieving a 15-point
decrease in CDAI score after 4 weeks of
treatment compared to baseline (derived, see
Section 3.6)  | <pre># patients and % /category (2 categories:
Achieving/Not achieving decrease)</pre>   |
| DAS28 calculated (DAS28YN)  | # patients and % /category, by visit
(2 categories: Yes/no)   |
| DAS28 score (DAS28)   | n, mean (95% CI), sd, median, min, max,
by visit  |
| DAS28 change from baseline to week 4 (derived, see Section 3.6)   | n, mean (95% CI), sd, median, min, max, by
visit  |
| Proportion of subjects achieving a change in
DAS28 from DAS28 > 3.2 to DAS28 ≤ 3.2 at week
4 compared to baseline (derived, see Section 3.6)  | <pre># patients and % /category (2 categories:
Achieving/Not achieving change)</pre>   |
| HAQ-DI questionnaire completed (HAQDIYN)  | # patients and % /category, by visit
(2 categories: Yes/no)   |
| HAQ-DI questionnaire Date (HAQDIDT)   | Listing only   |

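### SAP 3.6 tests the ACR20/50/70 joint criterion on one sum of SJC and TJC, an undeclared rule that is looser than the better reading of protocol 21.3.8

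*SAP*

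**What the plan says.** Protocol 21.3.8 defines ACR20/50/70 as at least 20%, 50% and 70% "improvement, respectively, in swollen and tender joint counts (SJC/TJC) and 3 of the following 5 assessments". It does not mention adding the counts.

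The protocol does add them for another secondary endpoint, in sections 14.2 and 23.5.2: "Proportion of subjects achieving a reduction of more than 10 (ten) swollen and/or tender joints (SJC and TJC, summarized) at week 4".

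SAP 3.6 carries the added count into ACR. Its 20% joint indicator is "≥20% improvement (reduction) in swollen and tender joint counts (SJC and TJC summarized) at week 4 compared to baseline", the 50% and 70% indicators are worded the same way, and the ACR definition that follows uses them. No separate SJC or TJC indicator is built for ACR.

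In this SAP, summarizing means adding. Section 2.1.6 says "The number of swollen and/or tender joints are found by summarizing SJC and TJC", and the table in section 6.1.2 lists a "Total number of tender or swollen joints (SJC and TJC summarized").

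SAP 1.1 promises that deviations from the protocol's methods will be explained in section 3.12. For ACR, section 3.12 explains only the week-4 time point, and it closes: "No other changes to analyses specified in the protocol have been identified at the time of writing this SAP".

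**The concern.** A requirement on two counts has become a requirement on one pooled percentage, in which the larger baseline count carries more weight. A patient with a large fall in tender joints can meet the joint criterion although swelling has not changed or has worsened. The mirror case also holds.

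This matters for an anti-inflammatory compound. Protocol 21.3.1 defines swelling as palpable synovitis, whereas tenderness depends on the subject's response to pressure and movement. Three of the five other ACR measures (patient global, pain and HAQ-DI) are patient-reported, so the remaining components do not force any improvement in SJC.

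The arms are small. With the planned minimum of 30 per group in the main study, one reclassified patient moves a rate by 1/30 = 3.3 points. With 15 per group in the sub-study, it moves a rate by 1/15 = 6.7 points.

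**Working it through.** The plan states no figure to reproduce, because this is an endpoint definition. The check compares the two rules.

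**1. Direction.** Let T and S be the baseline TJC and SJC, and let r_T and r_S be their proportional reductions at week 4. The reduction in the sum is

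r_sum = w·r_T + (1 − w)·r_S, with w = T/(T + S).

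This is a weighted average. If r_T ≥ x and r_S ≥ x, then r_sum ≥ x, but the converse fails. Enumerating baseline counts 1–30 and week-4 counts 0–30 at x = 0.20, 0.50 and 0.70 found no case that met both counts and failed the sum.

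**2. Worked patients.** All pass the SAP joint criterion and fail the two-count criterion.

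| Level | TJC | SJC | Sum | Fall in sum | Change in SJC |
|---|---|---|---|---|---|
| 20% | 20→12 | 10→10 | 30→22 | 8/30 = 26.7% | none |
| 20% | 20→12 | 8→9 | 28→21 | 7/28 = 25.0% | 1/8 = 12.5% worse |
| 50% | 16→3 | 10→10 | 26→13 | 13/26 = 50.0% | none |
| 70% | 28→1 | 10→10 | 38→11 | 27/38 = 71.1% | none |

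**3. When unchanged swelling can pass.** With SJC unchanged, the largest possible fall in the sum is T/(T + S). This reaches x only if T/S ≥ x/(1 − x): 0.2/0.8 = 0.25 at the 20% level, 0.5/0.5 = 1.0 at 50%, and 0.7/0.3 = 2.33 at 70%.

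**4. Illustrative size, joint criterion only.** The documents give no baseline counts or response distributions, so every input here is an assumption.

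- *Set A:* mean baseline TJC 16 and SJC 11, mean improvement 25% or 40%, SD 35 points, correlation between the two improvements 0.3 to 0.9. At the 20% level the excess (sum rule minus two-count rule) runs from 72.4 − 66.5 = 5.9 points to 57.4 − 37.3 = 20.1 points. At 50% it is about 4 to 16 points, and at 70% about 3 to 9.
- *Set B:* baseline TJC 18 (SD 8) and SJC 12 (SD 6), mean improvement 20% to 40%, SD 35 points, correlation 0.3 to 0.7. At the 20% level the excess is 11 to 21 points.

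**5. Who is added (set A).** Patients who pass the 20% sum rule with SJC unchanged or worse are about 0.6% to 6% of all patients. At 50% they are at most about 1%, and at 70% at most about 0.2%. As a share of the 20% excess, that is 0.6/5.9 = 10% to 6.2/20.1 = 31%. In every scenario more than half of the added patients improved on both counts, with one below the threshold.

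**6. Full ACR20.** Adding the 3-of-5 requirement to the set B assumptions, with the further assumption of correlations of 0.3 to 0.5 involving the other five measures, reduces the base-case ACR20 excess (mean improvement 30%, TJC–SJC correlation 0.5) from about 17 to about 11 points. With the TJC–SJC correlation extended to 0.9, it is about 3.5 to 15 points. This counts improvement in all five measures in the favourable direction. SAP 3.6 labels HAQ-DI improvement an increase, which needs its own check.

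**The case against.** The protocol never writes *each* or *both*, so a reader who takes it as an explicit two-count rule goes further than the text. The two-count reading is an inference. It is a strong one, because the counts are named without a sum here and summed expressly in 14.2 and 23.5.2. Even on the neutral view, the SAP settled the wording as a sum without saying so.

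A reader might also conclude that the resulting figures are not ACR rates at all, or are comparable with no other trial. That would need the external criterion, which the documents do not reproduce beyond section 21.3.8. Nor does SAP 3.12 assert that no other changes exist; it says none had been identified when it was written.

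Tenderness is not simply patient-reported. Under protocol 21.3.1 the assessor elicits it by pressure and manipulation and classifies each joint. SJC and TJC are also tabulated separately by visit in SAP 6.1.2, so a lack of effect on swelling would be visible at group level. That does not repair the responder definition.

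Finally, the rule applies equally to every arm. Nothing in the documents shows that it favours AP1189, and its effect on the difference between arms cannot be derived. These limits stand, but they do not remove the discrepancy.

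**Conclusion.** The point holds in this form: SAP 3.6 replaces the protocol's swollen and tender counts with one sum, does not declare it where SAP 1.1 says deviations are explained, and can therefore only add ACR responders relative to the two-count rule. The direction is algebraic and needs no assumption. The size is illustrative: roughly 6 to 21 percentage points on the joint criterion at the 20% level, and less for the full ACR20 rate.

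It would be wrong to infer that the added responders are mostly patients with unimproved swelling. They are a minority, and at the 70% level they need at least 2.33 tender joints per swollen joint at baseline.

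This should be fixed but does not threaten the main result. ACR is a secondary endpoint analyzed descriptively (protocol 14.2, 23.5.2). The primary endpoint and sample size rest on CDAI, and the interim choice of design rests on CDAI and safety.

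**What to change.** In SAP 3.6, replace each summed ACR joint indicator with two: a reduction of at least 20%, 50% or 70% in SJC, and separately in TJC. Define ACR20/50/70 as both met plus 3 of the 5 other assessments. Keep the sum only for the more-than-10-joints endpoint.

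If the sponsor also wants the summed version, report it alongside under a different label, and declare and justify it in SAP 3.12.

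The cost is a few lines of text and code, since both counts are already collected and tabulated. The reported ACR rates may be somewhat lower.

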| HAQ-DI responses (HAQDI1, HAQDI2, HAQDI3,
HAQDI4, HAQDI5, HAQDI6, HAQDI7, HAQDI8,
HAQDI9, HAQAID1, HAQAID2, HAQAID3,
HAQAID4, HAQAID5, HAQAID6, HAQAID7,
HAQAID8, HAQAID9, HAQHELP1, HAQHELP2,
HAQHELP3, HAQHELP4, HAQDI10, HAQDI11, | # patients and % /category, by visit
(4 categories for HAQDI items: Without any
difficulty/With some difficulty/With much
difficulty/Unable to do; 2 categories for
HAQAID and HAQHELP items: Used/not used) |

| HAQDI12, HAQDI3, HAQDI4, HAQDI5, HAQDI6,
HAQDI7, HAQDI8, HAQDI9, HAQD20, HAQAID10,
HAQAID11, HAQAID12, HAQAID13, HAQAID14,
HAQAID15, HAQAID16, HAQAID17, HAQHELP5,
HAQHELP6, HAQHELP7, HAQHELP8) |  |
|--|--|
| HAQ-DI pain because of illness past week, mm
(HAQPAIN)  | n, mean (95% CI), sd, median, min, max,
by visit  |
| HAQ-DI total score (derived, see Section 3.6)  | n, mean, sd, median, min, max,
by visit   |
| Change of HAQ-DI total score at week 4 compared to baseline (derived, see Section 3.6)   | N, mean, sd, median, min, max,
by visit   |
| FACIT Fatigue Scale completed (FACITYN)  | # patients and % /category, by visit
(2 categories: Yes/no)   |
| FACIT Fatigue Item responses (FACIT1, FACIT2,
FACIT3, FACIT4, FACIT5, FACIT6, FACIT7, FACIT8,
FACIT9, FACIT10, FACIT11, FACIT12, FACIT13)  | <pre># patients and % /category/item, by visit (5 categories per item; Not at all/A little bit/Somewhat/Quite a bit/Very much)</pre> |
| FACIT Fatigue total subscale score (derived, see Section 3.6)  | n, mean, sd, median, min, max,
by visit   |
| Change of FACIT-Fatigue total subscale score at week 4 compared to baseline (derived, see Section 3.6)   | n, mean, sd, median, min, max,
by visit   |
| Proportion of subjects achieving ACR response assessed by ACR 20 (derived, see Section 3.6)  | # patients and % /category (2 categories:
Achieving/Not achieving ACR 20)   |
| Proportion of subjects achieving ACR response assessed by ACR 50 (derived, see Section 3.6)  | # patients and % /category (2 categories:
Achieving/Not achieving ACR 50)   |
| Proportion of subjects achieving ACR response assessed by ACR 70 (derived, see Section 3.6)  | # patients and % /category (2 categories:
Achieving/Not achieving ACR 70)   |

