## 8.4 Calculated Data

- ✓ Calculated data will be checked for obvious discrepancies
- ✓ At least 20% of the data calculated for efficacy parameters (descriptive statistics, p-values, etc.) will be recalculated

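### SAP 3.6 labels HAQ-DI improvement as an increase, so the HAQ-DI component of ACR20, ACR50 and ACR70 is reversed as written

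*SAP*

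**What the plan says.** Section 3.6 of the SAP lists 18 indicators for the ACR response: six components, each at the 20%, 50% and 70% thresholds. The HAQ-DI line at the first threshold is "≥20% improvement (increase) in Health Assessment Questionnaire (HAQ-DI) total score at week 4 compared to baseline". The 50% and 70% lines carry the same direction. Joint counts, both global assessments, pain and CRP are all labelled as reductions.

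The list is operative. The SAP goes on: "The ACR response rates ACR20, ACR50, and ACR70 are defined as follows (using the indicators above". HAQ-DI is one of the five assessments of which three must improve alongside the joint counts. The results table in SAP 6.1.2 points back to the same place: "Proportion of subjects achieving ACR response assessed by ACR 20 (derived, see Section 3.6".

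The same section gives the HAQ-DI scoring. It includes this step: "Adjust for use of aids/help by increasing the category score from 0 or 1 to a 2 if use of aids/help for that category". The category scores are then summed and divided by the number of categories answered, with no reversal. In SAP 6.1.2 the item responses run from no difficulty to being unable to do the task.

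Protocol 21.3.8 requires improvement in each component and states no direction for HAQ-DI.

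**The concern.** Needing aids or help raises the score, and the worst response is inability to do the task. A higher HAQ-DI therefore means more disability, and improvement is a fall. The parenthesis in the three HAQ-DI lines says the opposite.

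A program that follows the text gives no HAQ-DI credit to a subject whose function improves, and gives credit to one whose function worsens by the threshold. Some true responders would be counted as non-responders, and some non-responders as responders. ACR20/50/70 are named secondary endpoints. ACR response also defines the groups in the exploratory cytokine Tables 11.4.1.76 to 11.4.1.80, listed in SAP Appendix 5.

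Nothing in the current text repairs this. Section 3.12 lists the departures from the protocol and closes with "No other changes to analyses specified in the protocol have been identified at the time of writing this SAP", without mentioning HAQ-DI direction. Appendix 5 records many edits to section 3.6, none of them to these lines.

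**Working it through.** The plan states no ACR rate or ACR-based sample size, so there is no figure to reproduce. The check covers the direction, when it matters, and how much one subject weighs.

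**1. Labels.** 6 components × 3 thresholds = 18 indicators. Five components × 3 = 15 say reduction; 1 × 3 = 3 say increase.

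**2. Worked cases.** Percent change = (week 4 − baseline) / baseline.
- 1.50 to 0.75: −0.75/1.50 = −50%. Read as a reduction, this meets the 20% and 50% indicators. As written, it meets none.
- 1.00 to 1.25: +0.25/1.00 = +25%. Read as a reduction, this meets none. As written, it counts toward ACR20.

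**3. When HAQ-DI decides the outcome.** Take a subject who meets the joint criterion. Three of five assessments are needed, so HAQ-DI decides only if exactly two of the other four are met.
- The other four have 2⁴ = 16 met/not-met patterns, and C(4,2) = 6 have exactly two met. In those six, a true improver on HAQ-DI is lost, and a subject who worsens by the threshold becomes a false responder.
- Of the C(5,3) = 10 ways to meet exactly three of five, C(4,2) = 6 include HAQ-DI and lose response. Responders meeting four or five keep it, since at least three others remain.

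These are counts of patterns, not frequencies among subjects.

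**4. Ceiling.** The scoring steps imply a range of 0 to 3, reported in steps of 0.125, which gives 24 non-zero baselines. A rise of fraction t from baseline b needs (3 − b)/b ≥ t, that is b ≤ 3/(1 + t).

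| Threshold | 3/(1 + t) | Highest usable baseline | Baselines from which the rise is possible |
|---|---|---|---|
| 20% | 2.50 | 2.50 | 20 of 24 |
| 50% | 2.00 | 2.00 | 16 of 24 |
| 70% | 1.76 | 1.75 | 14 of 24 |

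A reduction of each size is possible from all 24. The most disabled subjects could never meet the indicator as written.

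**5. Weight of one subject.** Protocol 23.2.1 plans at least 30 per arm and 23.2.2 at least 15 per sub-study arm. 1/30 = 3.3 points and 1/15 = 6.7 points. In a pooled main-plus-sub-study arm of 30 + 15 = 45 it is 2.2 points.

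**6. Illustration under assumed values.** None of these inputs is in the documents. Among subjects meeting the joint criterion, let each of the other four assessments be met independently with probability p, and let HAQ-DI improve past the threshold with probability h and worsen past it with probability w, independently of the rest.

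Rate = P(≥3 of 4) + P(exactly 2 of 4) × h with the right direction, and the same with w in place of h as written. The loss is 6p²(1 − p)² × (h − w).

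With h = 50% and w = 10%:
- p = 0.3: 21.6% becomes 11.0%
- p = 0.5: 50.0% becomes 35.0%
- p = 0.7: 78.4% becomes 67.8%

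Across p from 0.3 to 0.7 and h/w from 40%/20% to 60%/5%, the loss runs from 0.2646 × 0.20 = 5 points to 0.375 × 0.55 = 21 points.

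**The case against.** The strongest reply is that each line says improvement first and increase only in parentheses. The ACR definition and the protocol also speak of improvement, and a programmer who knows the instrument would code a fall. On that view the text contradicts itself without being plainly reversed. This is fair as to what may have happened in practice. But the parenthesis is the only direction stated for HAQ-DI, and the response is built from those lines. A programmer must either follow it or override it without a record. The text needs correcting in both cases.

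A second reply is that quality control would catch it. SAP 8.4 promises "At least 20% of the data calculated for efficacy parameters (descriptive statistics, p-values, etc.) will be recalculated", but recalculating from the same definition returns the same answer. SAP 8.2 and 8.4 also provide for checking that derived data sets hold the intended data and for looking for obvious discrepancies. Those checks could expose an improver flag beside a positive HAQ-DI change, but they do not guarantee it.

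Third, the effect on results is unproven. The table specifications are in a separate document and no program is visible. This stands. A false responder would also have to worsen on HAQ-DI while improving on joints and two other assessments. The documents give no frequency for that, and the two kinds of error partly offset within an arm.

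Finally, ACR response is secondary and descriptive. This also stands and limits the weight of the point.

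**Conclusion.** The concern holds. Three lines of SAP 3.6 give HAQ-DI a direction that contradicts the SAP's own scoring, and ACR20/50/70 are built from those lines. The direction follows from the aids/help rule and the order of the item responses, so the numeric codes in the annotated CRF are not needed to settle it.

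Only the HAQ-DI component is reversed, not the whole ACR endpoint: three of the other four assessments can still give a response. Any effect on results depends on the program having followed the text. The pattern counts, the ceiling (given the implied 0 to 3 range) and the points per subject are exact. The 5 to 21 point loss is conditional on the joint criterion and rests on assumed values.

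The primary CDAI endpoints, DAS28 and the mean HAQ-DI change are unaffected. The interim efficacy tables listed in SAP 3.7 are CDAI tables, so the choice of Part 2 design is unaffected too. This should be fixed, but it does not threaten the main conclusions.

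**What to change.** In SAP 3.6, replace increase with reduction in the three HAQ-DI indicator lines and log the correction in the revision history. Check the ACR program against the corrected text. If it followed the written label, re-derive ACR20, ACR50 and ACR70 and rerun Tables 11.4.1.76 to 11.4.1.80. If it already coded a fall as improvement, no result changes.

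The cost is three words and one program check. No new data are needed.
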